#### 11.16 Sample Shipment

All laboratory testing samples are to be shipped overnight in designated temperature conditions to the central laboratory where samples will be analyzed.

All frozen serum/plasma and nasal fluid for biomarkers are to be shipped monthly on dry ice to the central laboratory. Shipments should be made only on Mondays and Tuesdays to ensure receipt of the specimens by Friday.

#### 12 SAFETY ASSESSMENTS

#### 12.1 Compliance

At Randomization visit (V3), study personnel will be asked to take out all study medication bottles from the carton, weigh the bottles and record the weight. At each subsequent visit, study personnel will need to weigh the bottle without the carton and record weight. In addition, weight

measurements will be performed with the protection cap and safety clip from each bottle removed. This procedure should be followed every time study medication returned and weighed.

Participants will be asked to bring study medication with them to selected scheduled visits (V4, V5, V6, and Unanticipated Visit if necessary) after delivery of IP at V3. Each site participating in the trial will be instructed to assess subject's compliance by weighing the investigational product and obtaining the weight of the bottle in grams pre and post application during preventive treatment (all 3 unused bottles at visit V3 before the on-site first dose, after priming of first bottle at V3, after 4 weeks dosing of first bottle at V4, after 4 weeks dosing of second bottle at V5, and after 4 weeks dosing of third bottle at V6). Sites will be provided scales, which will be calibrated prior to each use. Study personnel will be instructed to record measurements into the eCRF.

## 12.2 Safety Monitoring

Local and systemic adverse events (AEs) related to intransal route of administration during prevention treatment and follow-up will be recorded for the duration of the study from screening to end of follow-up.

Safety monitoring will include infectious complications related to B244 (by symptoms and/or testing; pulmonary, nasal, neurological), local and systemic AEs related to intranasal route during treatment and at follow-up. Local AEs include runny nose, nasal congestion, sneezing, nasal itching, palate itching, anosmia, nasal ulceration, nasal bleeding, sore throat, cough, Bell's palsy, other neurologic complications, fevers, chills, headache, muscle aches, decreased appetite, nausea, vomiting, and rash.

Sponsor will distinguish between immediate (onset of reaction is during the first 30 minutes after administration) and delayed (onset of action is after the first 30 minutes of administration) effects for safety reporting of adverse events.

# 12.3 Pregnancy Reporting

Any pregnancy will be reported by study participants during their study participation. Participants who report pregnancy or lactation during the review of inclusion/exclusion criteria prior to randomization will not be enrolled in the trial. In case of pregnancy, Investigational Product should be discontinued and the Sponsor informed. Follow-up of the pregnancy will be mandatory until the outcome is available.

## 12.4 Study Completion

A completed participant is one who has completed all study visits. Day 112 (Week 16) study visit is defined as the participant's last visit (V7).

## 12.5 Subject Withdrawal Criteria

A subject may withdraw from the study at any time at his/her own request, or may be withdrawn at any time at the discretion of the Investigator for safety, behavioral, or administrative reasons.

Reasons for withdrawal (subjects who refuse to return for any remaining study visits) or discontinuation (subjects who prematurely stop the application) at any time during the study may include, but are not limited, to the following:

For safety reasons, either at the discretion of the Investigator or at the subject's request For protocol violations at the discretion of AOBiome

Due to concomitant therapy that could interfere with the results of the study (the Investigator will report all such information on the CRFs and decide, in accordance with AOBiome, whether the subject is to be withdrawn).

All premature discontinuations and their causes must be carefully documented by the Investigator on the CRF or if needed on the AE form.

If, for any reason, a subject is withdrawn before completing the final visit, the reason for termination will be entered on the CRF. All data gathered on the subject prior to termination will be made available to AOBiome. Subjects not completing the entire study should be fully evaluated when possible. The appropriate CRFs should be completed.

If the subject chooses to withdraw before completing the study, the subject should notify the study coordinator who will instruct the subject on completion of assessments for Unanticipated/Early Termination visit (Appendix A). For subjects who refuse to complete the assessments for their early termination, every attempt must be made to check on their status, using any mode of communication such as telephone, email, fax, or text.

## 13 EFFICACY ASSESSMENTS

Efficacy endpoints will be descriptively summarized and will include the number of observations, mean, median, standard deviation, minimum, and maximum of scores/values at all applicable time points and for all treatments in the ITT and PP Population.

For preventive treatment, the following secondary efficacy assessments will be obtained:

- Mean change in monthly migraine days from baseline to 12 weeks of treatment.
- Proportion of subjects experiencing a 50%, 75%, and 100% reduction in monthly migraine days from baseline to 12 weeks of treatment.
- Mean change in monthly migraine attacks from baseline to 12 weeks of treatment.
- Mean change in monthly acute migraine specific medication days from baseline to 12 weeks of treatment.
- Mean change in monthly moderate and severe headache days (migraine pain-intensity score) from baseline to 12 weeks of treatment.
- Mean change in monthly headache days from baseline to 12 weeks of treatment.
- Mean change in monthly headache hours from baseline to 12 weeks of treatment.

- Mean change from baseline to 12 weeks of treatment in disability, as measured by the Migraine Disability Assessment (MIDAS) questionnaire.
- Mean change from baseline to 12 weeks of treatment in monthly Headache Impact Test-6 (HIT-6) questionnaire.
- Mean change from baseline to 12 weeks of treatment in monthly Migraine Specific Quality of Life questionnaire (MSQL) questionnaire.
- Mean change in baseline Clinical Global Impression (CGI) score to end of treatment period.

For preventive treatment, the following exploratory efficacy assessments will be obtained:

- Changes in cytokine concentration in nasal fluid and blood from baseline to 12 weeks of treatment.
- Mean change in migraine days from end of treatment (last month of 12 weeks of treatment) to follow-up.
- Mean change in migraine associated symptoms: nausea/vomiting, photophobia and sonophobia from baseline to 12 weeks of treatment.

For the continuous endpoints of the change in migraine days, the change in migraine attacks, the change in days using rescue medication, the change in headache days, the change in headache hours, and the change in MIDAS, HIT-6, MSQL, and CGI scores, a one-sided two-sample equal-variance z-test will be used to compare treatment group means. Fisher's Exact test will be used to make treatment group comparisons on efficacy outcomes including the following binary outcomes:

• Proportion of subjects experiencing a 50%, 75%, and 100% reduction in monthly migraine days from baseline to 12 weeks of treatment.

Exploratory endpoints will be analyzed using the same method as for continuous efficacy endpoints. The analyses will be performed on the ITT and PP population.

## 14 STATISTICAL CONSIDERATIONS

## 14.1 Sample Size

Approximately 303 subjects will be enrolled in order to achieve a target sample size of 264 (i.e., 88 subjects per arm), allowing for a 10-15% drop-out rate.

Group sample sizes of 88 per arm achieve 80% power to reject the null hypothesis of equal means when the population means means

### 14.2 Populations for Analysis

Male and female subjects, 18 to 65 years of age, with a history of episodic migraine are eligible for enrollment.

ITT: includes all randomized participants who receive at least 1 dose of study medication.

Safety: includes all subjects who received at least 1 dose of study medication.

Per Protocol: subjects who administered at least 50 % of IP (based on the weight of IP used), have completed their Week 12 visit, and did not have any major protocol violations.

## 14.3 Data Analysis

The analyses will be conducted on all participant data when the trial ends. Data will be presented by treatment group and overall.

Categorical variables will be summarized by frequency distributions (number and percentages of subjects) and continuous variables will be summarized by descriptive statistics (mean, standard deviation etc).

Adverse events will be summarized by treatment using the Medical Dictionary for Regulatory Activities (MedDRA) system organ class and preferred term. Separate tabulations will be produced for all treatment-emergent AEs (TEAEs), treatment-related AEs (those considered by the Investigator as at least possibly drug related), SAEs, discontinuations due to AEs, and AEs Grade 3 [contact] provided for any deaths, SAEs, and AEs leading to discontinuation.

Descriptive statistics will be provided for clinical laboratory values (e.g., hematology, serum chemistry, and urinalysis) and vital signs data, presented as both actual values and changes from baseline relative to each on-study evaluation. Abnormal clinical laboratory values will be listed.

All data will be provided in by-subject listings.

#### 14.3.1 Disposition

A tabulation of the disposition of subjects will be presented, including the number enrolled, the number randomized, the number treated, and the reasons for study discontinuation will be reported. Summaries of the number in each analysis set will be summarized. Entry criteria and protocol deviations will be listed.

## 14.3.2 Demographic and Baseline

Demographic and baseline characteristic data summarization will be performed in order to descriptively assess the comparability of the treatments. Data to be tabulated will include age, race, ethnicity, height, weight, and BMI, as well as baseline characteristics related to medical history.

### 14.4 Safety Analyses

The primary endpoint is safety, as assessed by incidence and severity of AEs, physical examination, neurological examination, and vital signs (blood pressure, heart rate, respiratory rate). A secondary safety endpoint is safety assessments after 28 day follow-up period.

The analysis of safety will be based on the safety population, which is defined as all subjects receiving at least 1 dose of B244 or Vehicle. Adverse events (AEs) will be coded using the Medical Dictionary for Regulatory Activities (MedDRA®) for purposes of summarization. All AEs occurring during the study will be included in by-subject data listings and tabulated. Events leading to death, serious AEs, and events resulting in study discontinuation will be summarized using standard descriptive statistics, and presented by treatment arm. Exposure to study drug and reasons for discontinuation of study treatment will be tabulated. Shift tables relative to the normal range will be provided for laboratory parameters. Additional analyses will be performed, if warranted, upon review of the data.

#### 14.4.1 Definitions

All adverse events recorded during the study will be coded according to Medical Dictionary for Regulatory Activities.

The primary analysis of safety will be based on the safety population, which is defined as all subjects receiving at least 1 dose of B244 or placebo. Adverse events (AEs) will be coded using the Medical Dictionary for Regulatory Activities (MedDRA®) for purposes of summarization. All AEs occurring during the study will be included in by-subject data listings and tabulated. Events leading to death, SAEs, and events resulting in study discontinuation will be summarized using standard descriptive statistics, and presented by treatment arm. Exposure to study drug and reasons for discontinuation of study treatment will be tabulated. Shift tables relative to the normal range will be provided for laboratory parameters. Additional analyses will be performed, if warranted, upon review of the data.

#### 14.4.2 Adverse Events

All adverse events (AEs) recorded during the study through the date of randomization through 28 days after the last dose of study drug will analyzed.

All AE's will be coded according to Medical Dictionary for Regulatory Activities and summarized using System Organ Class (SOC) and Preferred Term (PT).

AE's will be summarized using incidence rates. Therefore, each subject will only contribute once for a given adverse event SOC or PT.

A summary of the incidence of any adverse event, SAE, and adverse events leading to discontinuation will be presented. Summaries will display, by treatment, the incidence of patients with events, the frequency of patients with events within each primary system organ class and by preferred terms. For each preferred term and each system organ class a patient

will be counted only once. For summaries on severe or drug-related AE, for a given patient, the highest severity or relationship for a specific preferred term will be considered.

#### 14.4.3 Deaths and Serious Adverse Events

Serious adverse events and events leading to death will be summarized overall and by primary system organ class and preferred term.

## 14.4.4 Adverse Events Leading to Treatment Discontinuation

Adverse events leading to treatment discontinuation will be summarized overall and by primary system organ class and preferred term.

## 14.5.1 Handling of Dropouts or Missing Data

Missing data will not be imputed for analysis.

Subjects who dropout after enrollment but prior to randomization will be replaced.

#### 14.6 Clinical Trial Protocol Deviations

All the following deviations will be summarized on the all randomized patient population:

- Inclusion or exclusion criteria not satisfied.
- Deviations related to the Investigational Product administration
- Not permitted concomitant medications.

### 15 ADVERSE EVENTS (AE) AND SERIOUS ADVERSE EVENTS (SAE)

The Investigator and study staff are responsible for detecting and recording AEs and SAEs during scheduled safety evaluations and whenever such information is brought to their attention. This section of the protocol provides definitions and detailed procedures to be followed.

#### 15.1 Definition of an AE

An AE is any untoward medical occurrence in a study participant which is temporally associated with the use of a medicinal product, regardless of its potential relationship to the medicinal product. An AE, therefore, can be any unfavorable or unintended sign, including an abnormal symptom, or disease (new or exacerbated), whether or not related to the investigational product (IP).

## Examples of an AE include:

Exacerbation of a pre-existing condition including either an increase in frequency and/or intensity of the condition.

New conditions detected or diagnosed after investigational product administration even though it may have been present prior to the start of the study.

Signs, symptoms of a drug interaction.

Signs, symptoms of a suspected overdose of either investigational product or a concurrent medication (overdose per se should not be reported as an AE/SAE).

AEs may include pre- or post-treatment events that occur as a result of protocol-mandated procedures (i.e., modification of participant's previous therapeutic regimen).

#### 15.2 Definition of a SAE

A serious adverse event is any untoward medical occurrence that, at any dose:

- (a) results in death.
- (b) is life-threatening.

NOTE: The term 'life-threatening' in the definition of 'serious' refers to an event in which the participant was at risk of death at the time of the event. It does not refer to an event, which hypothetically might have caused death, if it were more severe.

(c) requires hospitalization or prolongation of existing hospitalization.

NOTE: In general, hospitalization signifies that the participant has been detained (usually involving at least an overnight stay) at the hospital or emergency ward for observation and/or treatment that would not have been appropriate in the physician's office or out -patient setting. Complications that occur during hospitalization are AEs. If a complication prolongs hospitalization or fulfills any other serious criteria, the event is serious. When in doubt as to whether "hospitalization" occurred or was necessary, the AE should be considered serious. Routine hospitalizations or elective surgeries are generally not regarded as SAEs.

(d) results in disability/incapacity, or

NOTE: The term disability means a substantial disruption of a person's ability to conduct normal life functions. This definition is not intended to include experiences of relatively minor medical significance such as uncomplicated headache, nausea, vomiting, diarrhea, influenza, and accidental trauma (e.g. sprained ankle) which may interfere or prevent everyday life functions but do not constitute a substantial disruption.

- (e) is a congenital anomaly/birth defect
- (f) Medical or scientific judgment should be exercised in deciding whether reporting is appropriate in other situations, such as important medical events that may not be immediately life-threatening or result in death or hospitalization but may jeopardize the participant or may require medical or surgical intervention to prevent one of the other outcomes listed in the above definition. These should also be considered serious. Examples of such events are invasive or malignant cancers, intensive treatment in an emergency room or at home for allergic bronchospasm, blood dyscrasias or convulsions that do not result in hospitalization, or development of drug dependency or drug abuse.

## 15.3 Time Period, Frequency, and Method of Detecting AEs and SAEs

All AEs occurring after administration of the first dose of study medication and on or before the final assessment must be reported as AEs. All AEs must be recorded irrespective of whether they are considered drug-related.

At each assessment in the period defined above, AEs will be evaluated by the Investigator and recorded.

Any AEs already documented at a previous assessment and designated as ongoing, should be reviewed at subsequent assessments as necessary. If these have resolved, this should be documented. Changes in intensity or frequency of AEs should be recorded as separate events (i.e., a new record started).

The recording of AEs and SAEs are described in Section 15.4 ("Recording of AEs and SAEs").

#### 15.4 Recording of AEs and SAEs

All clinical events, including either observed or volunteered problems, complaints or symptoms are to be recorded on the Adverse Events page(s) of the CRF. The need to capture this information is not dependent upon whether the clinical event is associated with study treatment. Adverse clinical events resulting from concurrent illnesses or reactions to concurrent medications are also to be recorded. In order to avoid vague, ambiguous, or colloquial expressions, the AE should be recorded in standard medical terminology rather than the participant's own words.

Each adverse clinical event is to be evaluated for duration, intensity, and whether the event may be associated with the investigational product (IP) or other causes. Start and stop dates,

relationship to investigational product (IP), medical management, and alternative causality of event must be recorded in the Adverse Events section of the CRF. AEs believed to be possibly related to investigational product (IP) must be followed until resolution.

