#### 4 ENDPOINTS

## 4.1 Primary

• Safety as assessed by incidence and severity of AEs, physical examination, neurological examination, and vital signs (blood pressure, heart rate, respiratory rate).

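### Sections 15.4 and 12.2 conflict with the AE definition in 15.1 on whether an ordinary migraine attack is an AE, so part of the primary safety endpoint can reflect the study disease

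*Protocol*

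**What the plan says.** The primary endpoint (4.1) is "Safety as assessed by incidence and severity of AEs, physical examination, neurological examination, and vital signs". Four parts of the protocol bear on what enters its AE component.

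- **15.4, recording.** "All clinical events, including either observed or volunteered problems, complaints or symptoms are to be recorded" on the AE page of the CRF. Causality is no filter: "The need to capture this information is not dependent upon whether the clinical event is associated with study treatment". Concurrent illness is included: "Adverse clinical events resulting from concurrent illnesses or reactions to concurrent medications are also to be recorded".
- **12.2, safety monitoring.** The list of local AEs ends with "fevers, chills, headache, muscle aches, decreased appetite, nausea, vomiting, and rash". The section also asks for effects in the first 30 minutes after dosing to be distinguished from later ones.
- **15.1, definition and examples.** The definition speaks of a disease that is new or has worsened. The first example is "Exacerbation of a pre-existing condition including either an increase in frequency and/or intensity of the condition".
- **14.4.2, analysis.** AEs are summarised as incidence, so that "each subject will only contribute once for a given adverse event SOC or PT". The window runs "through the date of randomization through 28 days after the last dose of study drug". For summaries of severe AEs, the highest severity per preferred term is used.

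Subjects must have 4 to 14 migraine days per month in the baseline period (6.3). Nausea and/or vomiting is one of the protocol's own migraine criteria (11.10). Migraine and headache days are recorded daily in the electronic diary, and the associated symptoms are an exploratory efficacy endpoint (4.3).

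**The concern.** A site that takes 15.4 at its word, and sees headache, nausea and vomiting listed in 12.2, has grounds to enter each reported migraine attack as an AE. A site that works from 15.1 has equally good grounds to enter none unless the pattern worsens. Both are following the protocol.

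Three consequences are possible for the affected rows of the AE tables:

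- Incidence is raised in every arm by a disease that all subjects have, which shrinks the visible contrast for headache or nausea that the product may cause.
- The rate depends on how each site reads the text.
- If some but not all attacks are entered, an arm with fewer migraines shows fewer AEs, and efficacy looks like a safety advantage.

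Severity is exposed as well. The AE grade Severe in 15.5.1 is described in terms of incapacity, close to pain score 3 in 11.11, so ordinary severe attacks could fill the severe-AE table. This is an instruction on what goes on the CRF. An analysis plan cannot recover attacks that were not entered, nor reliably separate usual migraine from product-related headache coded to the same term.

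**Working it through.** The protocol states no AE rate, so there is no figure to reproduce. The check has a textual part and an illustrative part.

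**Text, side by side**

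| Question | 15.4 with 12.2 | 15.1 |
|---|---|---|
| Usual attack, unchanged pattern | Record: every complaint or symptom | Implied no: neither new nor worse |
| Nausea or vomiting within an attack | Record: also a listed local AE | Implied no |
| Worsened frequency or intensity | Record | Record |

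The sections agree only on the last row. The other place that mentions uncomplicated headache, nausea and vomiting is 15.2, which removes them only from the disability criterion for an SAE.

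**How often the disease could supply an AE**

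Inputs from the protocol: 4 to 14 migraine days per month (6.3); assumed mean reductions of 2.3 days on vehicle and 3.8 on active (sample size statement in the summary); 12 weeks of treatment, taken as three 4-week months.

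Assumptions: migraine days follow a Poisson distribution; baseline is uniform on the whole numbers 4 to 14; each migraine day reaches the AE page with probability r. None of these is a document figure.

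1. At unchanged frequency: 3 × 4 = 12 to 3 × 14 = 42 migraine days per subject in 12 weeks.
2. At the entry minimum with the vehicle reduction: 4 − 2.3 = 1.7 per month; 3 × 1.7 = 5.1; P(at least one) = 1 − exp(−5.1) = 99.4%.
3. Over the assumed baseline distribution, P(at least one recorded) = mean of 1 − exp(−3·m·r), where m = baseline − reduction:

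| r | Vehicle (−2.3) | Active (−3.8) | Difference |
|---|---|---|---|
| 1 | 99.9% | 94.8% | 5.1 points |
| 0.25 | 95.2% | 85.2% | 10.0 points |
| 0.10 | 79.7% | 68.2% | 11.5 points |

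The last column contains no product toxicity or protection; it comes only from the assumed efficacy difference. It is wider when recording is partial than when it is complete.

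**Loss of contrast**

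Let q be the share of subjects with a disease event entered as an AE, equal in the two arms and independent of product effects, and let p be the true product-emergent incidence. Observed incidence is q + (1 − q)p, so any true difference is multiplied by (1 − q). It is halved at q = 0.5 and reduced to a tenth at q = 0.9.

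**The case against.** The strongest reply is that the protocol already answers the question. The definition in 15.1 limits disease to what is new or worse, and 15.4, by its title, tells sites how to record events that already qualify as AEs; its later sentences speak of adverse clinical events. It covers observed or volunteered complaints, whereas migraine is solicited through a separate diary, and nothing sends diary entries to the AE page. The list in 12.2 concerns effects of the intranasal route, not every attack.

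This is a fair reading and probably the intended one. It does not close the matter. The definition is permissive and also covers an abnormal symptom, the opening of 15.4 is wider than AEs, and subjects may well volunteer at a visit what they have entered in the diary. No sentence makes 15.1 prevail.

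Other parts of the reply stand in full:

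- Safety is summarised descriptively (14.3, 14.4), with no between-arm AE test. A reader might infer a loss of power for the safety comparison; the document plans no test to which such a figure could apply, and AE rates for it would have to be invented.
- A reader might also infer that the whole primary endpoint is saturated. It is not. Nasal bleeding, congestion, ulceration, anosmia and cough keep their own preferred-term rows. SAEs, discontinuations due to AEs and treatment-related AEs are tabulated separately. Examinations and vital signs are further components.
- The arithmetic shows that subjects go on having migraines, not that sites will enter them.

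**Conclusion.** The point holds as a conflict between stated recording rules with a limited reach. What can be distorted is the incidence and severity of any AE, of headache or migraine, and of nausea or vomiting, together with the system organ class totals that contain them. Because AE incidence and severity come first in the primary endpoint, that is enough to justify a correction.

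The extent cannot be fixed from the document. It runs from none, if all sites work from 15.1, to nearly every subject, if all follow 15.4 literally. The percentages above depend on the Poisson model, the uniform baseline and the chosen recording probabilities, and are illustrations only. Near-complete inflation in all arms and a sizeable spurious safety advantage should not both be claimed at full strength: with each subject counted once, the second depends mainly on partial recording.

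**What to change.** Reconcile 12.2, 15.1 and 15.4 with one recording rule, repeated in the CRF completion guideline:

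- Migraine or headache attacks and their associated symptoms that are captured in the electronic diary at the subject's usual baseline pattern are efficacy data and are not entered as AEs.
- Any such event is still recorded as an AE if it is serious, new in character, worse in frequency or intensity than in the 28-day baseline, or considered by the investigator at least possibly related to the product, whether immediate or delayed.

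The relatedness clause should not be replaced by a time limit such as onset within 30 minutes of dosing. That could lose the delayed effects that 12.2 wants distinguished, and the diary items listed in 11.10 and Appendix A do not include headache onset relative to dosing.

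The cost is protocol wording and site guidance. The downside is an investigator judgement on worsening and relatedness, which the baseline diary already being collected can support.
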